
Study Endpoints:
 
Efficacy:
 
The primary efficacy endpoint is the change from baseline in non-vellus target area hair count (TAHC) using a microphotographic technique.
 
The secondary efficacy endpoints are defined as:
 
 
• development of new hair growth/scalp coverage as assessed by the investigator and the subject using a seven-point rating scale and subject global scalp photographs.
 
• Change from baseline in cumulative target area hair width (TAHW)
 
• Change from baseline in AGA stage according to the Norwood Hamilton scale in males and the Sinclair Scale in females
 
 
Safety:
 
Subjects will be assessed for local skin reactions and adverse events throughout the duration of the trial. In addition, vital signs, ECGs and clinical laboratory assessments will be performed on all subjects at the protocol defined time-points.

Statistical methods:
 
Summary descriptive statistics (N, mean, median, SD) by visit will be provided for all safety and efficacy parameters. The Intent to Treat population will be used for all efficacy assessments and the Safety population will be used for all safety assessments. No data imputation will be used. Primary and secondary efficacy parameters are described below:
 
Primary Efficacy Endpoints:
 
Mean change from baseline in non-vellus target area hair count (TAHC) will be quantified using a microphotographic technique and calculated along with the median, standard deviation, standard error, and 95% confidence limits around each mean change to allow tests of the null hypothesis that the population mean changes are zero.
 
Secondary Efficacy Endpoints:
 
Mean change from baseline in cumulative target area hair width (TAHW) will be quantified using a microphotographic technique and calculated along with the median, standard deviation, standard error, and 95% confidence limits around each mean change to allow tests of the null hypothesis that the population mean changes are zero.

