## **13. STATISTICS**

### **13.1. Statistical Methods**

Summary descriptive statistics (N, mean, median, SD) by visit will be provided for all safety and efficacy parameters. The Intent to Treat population will be used for all efficacy assessments and the Safety population will be used for all safety assessments. No data imputation will be used. Primary and secondary efficacy parameters are described in the sections below.

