### **13.3. Secondary Efficacy Endpoints**

Mean change from baseline in cumulative TAHW will be quantified using a microphotographic technique and calculated along with the median, standard deviation, standard error, and 95% confidence limits around each mean change to allow tests of the null hypothesis that the population mean changes are zero.

The seven-point rating scale to measure the investigator and subject assessment of the development of new hair growth/scalp coverage will be analyzed with summary statistics (N, mean, median, SD) for each visit where the assessment is made. Similar summary statistics will be used to analyze change from baseline in AGA stage separately for males (Horwood Hamilton Scale) and for females (Sinclair Scale) at each applicable visit.

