Visit	Statistic	Value	Change	Value	Change	Value	Change
D 1' a							
Baseline ^a	n	XX		XX		XX	
	Mean (SD)	xx.x(xx.xx)		xx.x (xx.xx)		xx.x(xx.xx)	
	SE	X.XX		X.XX		X.XX	
	Median	XXX.X		XXX.X		XXX.X	
	(Min, Max)	(xxx, xxx)		(xxx,xxx)		(xxx,xxx)	
V5 – Week 8	n	XX	XX	XX	XX	XX	xx
	Mean (SD)	xx.x (xx.xx)					
	SÈ	x.xx	X.XX	X.XX	x.xx	x.xx	x.xx
	Median	XXX.X	XXX.X	XXX.X	xxx.x	XXX.X	XXX.X
	(Min, Max)	(xxx,xxx)	(xxx, xxx)	(xxx,xxx)	(xxx,xxx)	(xxx,xxx)	(xxx,xxx)
	[95% CI] ^b	()	[xx.x, xx.x]	(,)	[xx.x, xx.x]	(;)	[xx.x, xx.x]
V7– Week 16	n	XX	XX	XX	XX	XX	XX
	Mean (SD)	xx.x (xx.xx)	xx.x (xx.xx)	xx.x (xx.xx)	xx.x(xx.xx)	xx.x (xx.xx)	xx.x (xx.xx)
	SE	x.xx	X.XX	X.XX	x.xx	X.XX	x.xx
	Median	XXX.X	XXX.X	XXX.X	xxx.x	XXX.X	xxx.x
	(Min, Max)	(xxx,xxx)	(xxx,xxx)	(xxx,xxx)	(xxx, xxx)	(xxx,xxx)	(xxx, xxx)
	[95% CI] ^b	())	[xx.x, xx.x]	()	[xx.x, xx.x]	()	[xx.x, xx.x]

 ^a Baseline is selected as the last measurement prior to the first application of study medication.
 ^b Confidence interval for the change from baseline.

Protocol: ATI-50002-AGA-201

Table 14.2.1.1 Non-Vellus Target Area Hair Count: Mean and Mean Change from Baseline (hairs/cm²) ITT Population

		Fen	nale	Ma	ale	To	tal
Visit	Statistic	Value	Change	Value	Change	Value	Change
V10-Week 26	n Mean (SD) SE Median (Min, Max) [95% CI] ^b	xx xx.x (xx.xx) x.xx xxx.x (xxx ,xxx)	XX XX.X (XX.XX) X.XX XXX.X (XXX ,XXX)	xx xx.x (xx.xx) x.xx xxx.x (xxx ,xxx)	XX XX.X (XX.XX) X.XX XXX.X (XXX, XXX)	xx xx.x (xx.xx) x.xx xxx.x (xxx ,xxx)	XX XX.X (XX.XX) X.XX XXX.X (XXX, XXX)
V16-Week 52	n Mean (SD) SE Median (Min, Max) [95% CI] ^b	xx xx.x (xx.xx) x.xx xxx.x (xxx ,xxx)	[xx.x, xx.x] xx xx.x (xx.xx) x.xx xxx.x (xxx, xxxx) [xx.x, xx.x]	xx xx.x (xx.xx) x.xx xxx.x (xxx ,xxx)	[xx.x, xx.x] xx xx.x (xx.xx) x.xx xxx.x (xxx, xxxx) [xx.x, xxxx)	xx xx.x (xx.xx) x.xx xxx.x (xxx ,xxx)	[xx.x, xx.x] xx xx.x (xx.xx) x.xx xxx.x (xxx, xxxx) [xx.x, xx.x]

^a Baseline is selected as the last measurement prior to the first application of study medication.

Repeat Format for

Table 14.2.1.2 Vellus Target Area Hair Count: Mean and Mean Change from Baseline (hairs/cm²) ITT Population

Table 14.2.1.3 Total (Non-Vellus + Vellus) Target Area Hair Count: Mean and Mean Change from Baseline (hairs/cm²) ITT Population

Table 14.2.1.4 Non-Vellus Target Area Hair Width: Mean and Mean Change from Baseline (cm) ITT Population

Table 14.2.1.5 Vellus Target Area Hair Width: Mean and Mean Change from Baseline (cm) ITT Population

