Table 14.2.1.6 Total (Non-Vellus + Vellus) Target Area Hair Width: Mean and Mean Change from Baseline (cm) ITT Population

 Table 14.2.1.7
 Average Non-Vellus Hair Width: Mean and Mean Change from Baseline (cm) ITT Population

Footnote for 14.2.1.7: Note: Average non-vellus hair width is calculated for each patient as the non-vellus target area count divided by the non-vellus target area hair width

^b Confidence interval for the change from baseline.

23 Apr 2019 Statistical Analysis Plan

Table 14.2.2.1 Investigator Global Assessment ITT Population

		ITT Population		
Visit	Statistic	Female	Male	Total
V5 – Week 8	n	XX	XX	VV
v 5 – vv eek o	Mean (SD)			XX
	` ,	xx.x (xx.xx)	xx.x (xx.xx)	xx.x (xx.xx)
	Median	xxx.x	XXX.X	XXX.X
	(Min, Max)	(xxx,xxx)	(xxx,xxx)	(xxx, xxx)
V7– Week 16	n	XX	xx	XX
	Mean (SD)	xx.x (xx.xx)	xx.x (xx.xx)	xx.x (xx.xx)
	Median	xxx.x	XXX.X	XXX.X
	(Min, Max)	(xxx,xxx)	(xxx,xxx)	(xxx,xxx)
V10-Week 26	n	XX	XX	XX
	Mean (SD)	xx.x (xx.xx)	xx.x (xx.xx)	xx.x (xx.xx)
	Median	XXX.X	XXX.X	XXX.X
	(Min, Max)	(xxx, xxx)	(xxx, xxx)	(xxx, xxx)
V13-Week 39	n	XX	XX	XX
	Mean (SD)	xx.x (xx.xx)	xx.x (xx.xx)	xx.x (xx.xx)
	Median	XXX.X	XXX.X	XXX.X
	(Min, Max)	(xxx,xxx)	(xxx,xxx)	(xxx,xxx)
V16 – Week 52	n	XX	XX	XX
	Mean (SD)	xx.x (xx.xx)	xx.x(xx.xx)	xx.x(xx.xx)
	Median	XXX.X	XXX.X	XXX.X
	(Min, Max)	(xxx, xxx)	(xxx, xxx)	(xxx, xxx)
FU/Early Termination	n	XX	XX	XX
1 C. Larry 1 Crimmunon	Mean (SD)	xx.x (xx.xx)	xx.x (xx.xx)	xx.x (xx.xx)
	Median	XXX.X	XXX.X	XXX.X
	(Min, Max)			
	(IVIIII, IVIAX)	(xxx ,xxx)	(xxx ,xxx)	(xxx, xxx)

Repeat Format for

 Table 14.2.2.2
 Subject Self-Assessment ITT Population

Aclaris Therapeutics Inc.

Protocol: ATI-50002-AGA-201

23 Apr 2019 Statistical Analysis Plan

Table 14.2.3.1
Investigator Global Assessment: Patients with Slightly Increased Hair Growth or Better (Grade +1 to +3)
ITT Population

Visit	Statistic	Female	Male	Total
V5 – Week 8	N^a n (%)	xx xx (xx.x)	xx xx (xx.x)	xx xx (xx.x)
V7- Week 16	N^a n (%)	xx xx (xx.x)	xx xx (xx.x)	xx xx (xx.x)
V10-Week 26	N^a n (%)	xx xx (xx.x)	xx xx (xx.x)	xx xx (xx.x)
V13-Week 39	N^a n (%)	xx xx (xx.x)	xx xx (xx.x)	xx xx (xx.x)
V16 – Week 52	N^a n (%)	xx xx (xx.x)	xx xx (xx.x)	xx xx (xx.x)
FU/Early Termination	N^a n (%)	xx xx (xx.x)	xx xx (xx.x)	xx xx (xx.x)

Repeat Format for

Table 14.2.3.2 Subject Self-Assessment: Patients with Slightly Increased Hair Growth or Better (Grade +1 to +3) ITT Population

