^a The number of patents with an assessement at the visit. Used as denominator for percentages.

Table 14.2.4
Improvement from Baseline in Norwood-Hamilton Scale in Males
ITT Population

Visit	=	Improved by ≥ 1 Level	Improved by ≥ 2 Levels	
Shift Detail ^a	N^b	n (%)	n (%)	
V7 – Week 16	XX	xx (xx.x)	xx(xx.x)	
IV – IIIa		xx (xx.x)	xx (xx.x)	
IV – III vertex		xx (xx.x)		
etc				
V10 – Week 26	XX	xx (xx.x)	xx (xx.x)	
IV – IIIa		xx (xx.x)	xx (xx.x)	
IV – III vertex		xx (xx.x)		
etc				
V16 – Week 52	XX	xx (xx.x)	xx (xx.x)	
IV – IIIa		xx (xx.x)	xx (xx.x)	
IV – III vertex		xx (xx.x)	, ,	
etc		` '		
FU/Early Termination ^c	XX	xx (xx.x)	xx (xx.x)	
IV – IIIa		xx (xx.x)	xx (xx.x)	
IV – III vertex		xx (xx.x)	,	
etc		,		
Early Term, 1st 26 Weeks	XX	xx (xx.x)	xx (xx.x)	
IV – IIIa		xx (xx.x)	xx (xx.x)	
IV – III vertex		xx (xx.x)	9	
etc		ini (mini)		

 $^{^{}a}$ The Baseline Score →Timepoint Score combination that met the ≥ 1 level improvement criteria.

^b The number of patients with a non-missing score baseline and at the visit indicated. Used as denominator for percentages.

^c Includes early terminations or follow-ups collected during the first 26 Weeks or during the additional six months for patients opting to continue treatment in the optional six month extension. Additional rows provided to further sub-divide based on the period (1st 26 Weeks vs 6 Month Extension) and termination status (early termination vs follow-up).

Protocol: ATI-50002-AGA-201

Table 14.2.4
Improvement from Baseline in Norwood-Hamilton Scale in Males
ITT Population

Visit Shift Detail ^a	N^b	Improved by ≥ 1 Level n (%)	Improved by ≥ 2 Levels n (%)	
E II 4st AC W		(()	
Follow-Up 1st 26 Weeks	XX	xx (xx.x)	xx(xx.x)	
IV – IIIa		xx (xx.x)	xx(xx.x)	
IV – III vertex		xx (xx.x)		
etc				
Early Term, 6 Month Extension	XX	xx (xx.x)	xx (xx.x)	
IV – IIIa		xx (xx.x)	xx (xx.x)	
IV – III vertex		xx (xx.x)		
etc				
Follow-Up, 6 Month Extension	XX	xx (xx.x)	xx (xx.x)	
IV – IIIa		xx (xx.x)	xx (xx.x)	
IV – III vertex		xx (xx.x)		
etc				

^a The Baseline Score → Timepoint Score combination that met the ≥ 1 level improvement criteria.

PROGRAMMING NOTE: Add rows for each combination that shows an improvement starting from greatest improvement and highest baseline score.

^b The number of patients with a non-missing score baseline and at the visit indicated. Used as denominator for percentages.

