^b The number of patients with a non-missing score baseline and at the visit indicated. Used as denominator for percentages.

^c Includes early terminations or follow-ups collected during the first 26 Weeks or during the additional six months for patients opting to continue treatment in the optional six month extension. Additional rows provided to further sub-divide based on the period (1st 26 Weeks vs 6 Month Extension) and termination status (early termination vs follow-up).

Protocol: ATI-50002-AGA-201

Table 14.2.6 Correlation of Selected Effiacy Measures ITT Population

Visit	Parameter → ↓	Change in Nonvellus Target Area Hair Count		Change in Nonvellus Target Average Area Hair Width	Investigator Global Assessment	Subject Self Assessment
V5 – Week 8	Change in Nonvellus Target Area Hair Count	Corr=1	Corr=0.xx P-Value=0.xxxx	Corr=0.xx P-Value=0.xxxx	Corr=0.xx P-Value=0.xxxx	Corr=0.xx P-Value=0.xxxx
	Change in Nonvellus Target Area Hair Width		Corr=1	Corr=0.xx P-Value=0.xxxx	Corr=0.xx P-Value=0.xxxx	Corr=0.xx P-Value=0.xxxx
	Change in Nonvellus Target Area Average Hair Width			Corr=1	Corr=0.xx P-Value=0.xxxx	Corr=0.xx P-Value=0.xxxx
	Investigator Global Assessment				Corr=1	Corr=0.xx P-Value=0.xxxx
V7–Week 16 V10–Week 26 V16 – Week 52						

Note: Correlations are Pearson Correlations

Table 14.2.7 Correlation of Nonvellus Hair Count and Width Measures with Time Since Diagnosis of Androgenetic Alopecia ITT Population

Visit	Parameter → ↓	Time Since Diagnosis of Androgenetic Alopecia	
V5 – Week 8	Change in Nonvellus Target Area Hair Count	Corr=0.xx P-Value=0.xxxx	
	Change in Nonvellus Target Area Hair Width	Corr=0.xx P-Value=0.xxxx	
	Change in Nonvellus Target Area Average Hair Width	Corr=0.xx P-Value=0.xxxx	
V7–Week 16 V10–Week 26 V16 – Week 52			

Note: Correlations are Pearson Correlations

Aclaris Therapeutics Inc.

Protocol: ATI-50002-AGA-201

23 Apr 2019 Statistical Analysis Plan

Table 14.3.1 Summary of Treatment-Emergent Adverse Events Safety Population

	Female (N=xx) n (%)	Male (N=xx) n (%)	Total (N=xx) n (%)
Any Adverse Event	xx (xx.x)	xx (xx.x)	xx (xx.x)
Any Treatment-Related Adverse Event	xx (xx.x)	xx (xx.x)	xx (xx.x)
Any Serious Adverse Event	xx (xx.x)	xx (xx.x)	xx (xx.x)
Any Adverse Event Resulting in Study Discontinuation	xx (xx.x)	xx (xx.x)	xx (xx.x)

n = number of patients with treatment emergent adverse event(s).

NOTE: Patients with multiple occurrences of a preferred term are counted only once for that term.

Table 14.3.1.1

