Appendix 16.2.2.3 Norwood-Hamilton Scale in Males

Patient	Visit	Assessment Date	Study Day ^a	N-H Score	Improvement from Baseline (Yes/No) ^c
VV VVV	V1 Caraanina	ddmmmraaa	WW	I	Yes/No
XX-XXX	V1 - Screening V2 – Day 1	ddmmmyyyy	XX XX	Π_{p}	I ES/INO
	V2 – Day 1 V7 – Week 16	ddmmmyyyy ddmmmyyyy	XX	II IIa	
	V10 – Week 16 V10 – Week 26	ddmmmyyyy		IIa III	
	V16 – Week 20 V16 – Week 52		XX	IIIa	
		ddmmmyyyy	XX		
	Early Term 1 st 26 Weeks Follow-Up 1 st 26 Weeks	ddmmmyyyy	XX	III Vertex IV	
	*			IV IVa	
	Early Term 6 Month Extension			Iva V	
	Follow-Up 6 Month Extension			·	
				Va VI	
				VI VII	

^a Assessment date – date of first application of study medication (+1 if ≥ first application of study medication).

Programming note: Differentiation between Early term and Follow-up is based on the availability of V10 (1st 26 Weeks) or V16 (patients entering extension) data for ANY data (not just Norwood-Hamilton). If a patient does not enter the extension and had no data collected for V10 and had discontinued the trial the follow-up is considered "Early Term 1st 26 Weeks". If they had V10 and did not enter the extension then it's "Follow-Up 1st 26 Weeks". Similarly for those entering extension, those without a V16 who discontinued the study are assigned "Early Term 6 Month Extension" and those with V16 are assigned to "Follow-Up 6 Month Extension".

^b Used as baseline for analysis.

^c Yes – score improved by ≥1 level including shifts in "sub-level" (e.g. IIIa to III is considered a 1 level improvement).

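### SAP Tables 14.2.4 and 14.2.5 tabulate only improvement in AGA stage; the mean, median and SD of change planned in Protocol 13.3, and separate counts of unchanged and worsened patients, are in no available summary shell

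*SAP*

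**What the plan says.** The endpoint has two directions. The Protocol Synopsis (Study Endpoints) lists as secondary "Change from baseline in AGA stage according to the Norwood Hamilton scale in males and the Sinclair Scale in females". Protocol 13.1 sets the general rule: "Summary descriptive statistics (N, mean, median, SD) by visit will be provided for all safety and efficacy parameters". Protocol 13.3 plans N, mean, median and SD for the seven-point ratings and then continues: "Similar summary statistics will be used to analyze change from baseline in AGA stage separately for males", with the same for females on the Sinclair scale, at each applicable visit.

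The SAP shells for this endpoint are Table 14.2.4 (men) and Table 14.2.5 (women). For each visit they have an N column and two result columns: n (%) improved by ≥1 level and n (%) improved by ≥2 levels. Footnote b defines N as "The number of patients with a non-missing score baseline and at the visit indicated" and makes it the denominator. The shift-detail rows are restricted by a programming note under both tables: "Add rows for each combination that shows an improvement starting from greatest improvement and highest baseline score".

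Listings 16.2.2.3 and 16.2.2.4 print each patient's score at each stage visit, with one derived column, "Improvement from Baseline (Yes/No").

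The other efficacy measures are handled differently. Table 14.2.1.1 gives hair-count value and change, with a footnoted "Confidence interval for the change from baseline". "Table 14.2.2.1 Investigator Global Assessment ITT Population" has n, mean, SD, median, minimum and maximum, and sits beside a separate table of patients rated as having increased growth (14.2.3.1).

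**The concern.** The protocol promises a summary of change; the shells deliver a summary of improvement. A patient who worsens stays in the denominator but is indistinguishable from one who is unchanged.

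That distinction is part of the efficacy result here. Protocol 5.1 describes hair loss in this condition as gradual, and there is no control arm. Every eligible baseline stage also has room to worsen: Sinclair grades 2, 3 and 4 lie on a scale that runs to 5, and Norwood-Hamilton III vertex, IV and V on one that runs to VII. Stage is rated by the treating investigator in an open-label study (Protocol 11.2), whereas hair counts are read by blinded technicians (Protocol 11.1). Stage is thus one of the less protected measures, and its tables show only the favourable direction.

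**Working it through.** There is no planned figure to reproduce. The check compares the two documents and then asks whether the shell content determines the planned statistics.

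**Step 1. Planned items against shells.**

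| Item for change in stage | Tables 14.2.4 / 14.2.5 |
|---|---|
| N with baseline and visit score | Present (footnote b) |
| Mean, median, SD of change | Absent |
| Improved by ≥1 and ≥2 levels | Present |
| Not improved (unchanged and worsened together) | Not printed, but equals N minus n improved |
| Unchanged | Cannot be derived |
| Worsened | Cannot be derived |

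Of the four statistics in Protocol 13.1 and 13.3, one is in the shells and three are not.

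**Step 2. Are the missing items elsewhere?** The available efficacy shells run from 14.2.1.1 to 14.2.7 without a gap in numbering. The 14.2.1 series covers hair count and width. The 14.2.2 and 14.2.3 series cover the investigator and subject ratings. Tables 14.2.6 and 14.2.7 are correlations that do not include stage. Table 14.1.2 gives stage at baseline only. The two listings hold the raw scores but count nothing, and their flag reads No for an unchanged and a worsened patient alike.

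**Step 3. Does the printed headline fix the result?** Inputs: N = 12 in one sex (Protocol 7.2), taking all 12 as scored. The outcomes are assumed for illustration. Change = visit minus baseline, so negative is better. Three patients improve by one Sinclair grade, w worsen by one grade, and the remaining 9 − w are unchanged.

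- Headline for any w: 3/12 = 25.0% improved by ≥1 level; 0/12 = 0.0% by ≥2 levels.
- Mean = (w − 3)/12.
- SD = √{[(3 + w) − 12 × mean²]/11}.

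| Worsened (w) | Shell headline (≥1; ≥2) | Mean | SD | Median |
|---|---|---|---|---|
| 0 | 3 (25.0%); 0 | -0.25 | 0.45 | 0 |
| 3 | 3 (25.0%); 0 | 0.00 | 0.74 | 0 |
| 6 | 3 (25.0%); 0 | +0.25 | 0.87 | +0.5 |
| 9 | 3 (25.0%); 0 | +0.50 | 0.90 | +1 |

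For w = 0: mean = -3/12 = -0.25; SD = √[(3 − 0.75)/11] = 0.45. For w = 6: mean = 3/12 = +0.25; SD = √[(9 − 0.75)/11] = 0.87.

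The shift rows do not separate these cases, because the same three improvements fill them each time. Identical printed tables are compatible with net improvement and with net worsening.

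**The case against.** The strongest reply is that little turns on this. Stage is a descriptive secondary endpoint with about 12 patients per sex, and Protocol 13.3 attaches no hypothesis test to it. Every score is listed, so a reader can count worsening by hand. The primary endpoint and both global ratings are summarised in both directions. A mean of an ordinal stage is debatable, and the available pages assign no numbers to the Norwood-Hamilton sub-levels. The protocol plans summary statistics, not shift tables. Finally, the part of the SAP that was not available may define a coding or explain the departure.

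Much of this stands as a limit on weight. It does not remove the discrepancy. Protocol 13.3 promises summaries, and a listing that flags only improvement is not one. Doubts about a mean are a reason to record a departure, but counting unchanged and worsened patients needs no mean. Tables of improved patients are unobjectionable beside a two-directional summary, as the SAP provides for the global ratings; stage lacks that companion.

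A reader might go further in three ways that the documents do not support:

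- That all four planned statistics are missing, or that nothing can be said about patients who did not improve. N is in the shells, and the combined number follows by subtraction.
- That worsening goes unreported. The raw scores are in the listings; what is missing is the summary.
- That the percentage improved is inflated by rating error of some known size. The documents give no error rate.

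**Conclusion.** The two shells are wrong as written against Protocol 13.1 and 13.3. Followed literally, they report a two-directional secondary endpoint in the favourable direction only. Missing are the mean, median and SD of change and the split between unchanged and worsened patients. In the example, 3/12 improved fits a mean change of -0.25 with none worsened and +0.25 with six worsened.

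The example assumes N = 12 with complete scores and one-grade changes. The finding itself rests only on the content of the shells. It is confined to those that were available, so it does not establish that the departure is unexplained. It should be corrected, but it does not touch the primary endpoint.

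**What to change.** 1. In Tables 14.2.4 and 14.2.5, add n (%) unchanged and n (%) worsened at each visit, on the footnote b denominator, and amend the programming note so that worsening combinations also get shift rows.
2. Add mean, median and SD of change by sex and visit, as Protocol 13.3 plans.
3. For men, pre-specify an ordinal coding of the Norwood-Hamilton levels and sub-levels. It should agree with footnote c of listing 16.2.2.3, which counts a sub-level shift (IIIa to III) as one level. The listing shows twelve levels from I to VII, and numbering them in that order would satisfy the footnote. The sample rows of Table 14.2.4 point the same way (IV to IIIa has an entry under ≥2 levels, IV to III vertex only under ≥1), but placeholders do not replace a stated rule.
4. If a mean of this scale is not wanted, document the departure from Protocol 13.3 and keep the improved / unchanged / worsened counts.

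The cost is a slightly longer table and minor programming. The scores are already scheduled and listed, so no new data are needed.

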**Safety Assessments:**

Data from all enrolled and treated subjects will be presented and summarized. Safety analyses will include descriptive statistics calculated on the safety parameters using the safety population. The proportion of subjects with treatment-emergent adverse events will be tabulated and presented by Medical Dictionary for Regulatory Activities (MedDRA) System Organ Class. Vital signs and clinically significant abnormal laboratory results will also be tabulated and presented. Clinical laboratory and ECG results will be tabulated, highlighting abnormal results. Local skin reaction results will be tabulated and summarized by visit.

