## **6. TRIAL OBJECTIVES AND PURPOSE**

### **6.1. Primary Objective**

The primary objective is to assess the safety, tolerability and efficacy of ATI-50002 Topical Solution, 0.46% in male and female subjects with AGA.

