#### **12.1.6. Local Skin Reactions**

Investigators and subjects will be required to assess the treated scalp area for local skin reactions (LSRs) at visits 2-11. The following signs and symptoms of contact dermatitis will be assessed:

- Stinging/Burning
- Itching
- Dryness
- Erythema
- Scaling

The Investigator and Subject should report the one integer that best describes the severity of each LSR sign or LSR symptom for the treated scalp area using the scale below.

Local Skin Reactions	
Grade	Descriptor
0	None
1	Mild
2	Moderate
3	Severe

**If a local skin reaction requires treatment or causes an interruption or discontinuation of study medication then the LSR needs to be recorded and assessed as an adverse event.**

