^a Missing is referring to an event that has missing severity and no other event with severity provided for the same preferred term.

NOTE: If a patient had more than one adverse event within an SOC, the patient was counted in the category of greatest known severity.

If a patient had multiple occurrences of the same adverse event, the patient was counted in the category of greatest known severity.

Table 14.3.1.7 Treatment-Emergent Study Medication Related Adverse Events by Maximum Severity Safety Population

PROGAMMING NOTE: Separate pages for Female. Male and Total.

Protocol: ATI-50002-AGA-201

Table 14.3.1.8 Local Skin Reactions – Highest Grade Any Time Post-Baseline Safety Population

		Highest Severity, n (%)								
	•		Fema	ale			Ma	ale		
Assessor	Sign	Mild	Moderate	Severe	Total	Mild	Moderate	Severe	Total	
Any	Any	xx (xx.x)	xx (xx.x)	xx (xx.x)	xx (xx.x)	xx (xx.x)	xx (xx.x)	xx (xx.x)	xx (xx.x)	
Investigator	Any	xx (xx.x)	xx (xx.x)	xx (xx.x)	xx (xx.x)	xx (xx.x)	xx (xx.x)	xx (xx.x)	xx (xx.x)	
_	Erythema	xx (xx.x)	xx (xx.x)	xx (xx.x)	xx (xx.x)	xx (xx.x)	xx (xx.x)	xx (xx.x)	xx (xx.x)	
	Scaling	xx (xx.x)	xx (xx.x)	xx (xx.x)	xx (xx.x)	xx (xx.x)	xx (xx.x)	xx (xx.x)	xx (xx.x)	
	Dryness	xx (xx.x)	xx (xx.x)	xx (xx.x)	xx (xx.x)	xx (xx.x)	xx (xx.x)	xx (xx.x)	xx (xx.x)	
Subject	Any	xx (xx.x)	xx (xx.x)	xx (xx.x)	xx (xx.x)	xx (xx.x)	xx (xx.x)	xx (xx.x)	xx (xx.x)	
_	Stinging/burning	xx (xx.x)	xx (xx.x)	xx (xx.x)	xx (xx.x)	xx (xx.x)	xx (xx.x)	xx (xx.x)	xx (xx.x)	
	Itching	xx (xx.x)	xx (xx.x)	xx (xx.x)	xx (xx.x)	xx (xx.x)	xx (xx.x)	xx (xx.x)	xx (xx.x)	

^a Percentages are based on the total number of patients safety population for the group.

NOTE: Patients are counted only once foreach sign at the highest severity grade.

Protocol: ATI-50002-AGA-201

Table 14.3.1.8 Local Skin Reactions – Highest Grade Any Time Post-Baseline Safety Population

_			Highest	Severity, n (%)
			Tot	al	
Assessor	Sign	Mild	Moderate	Severe	Total
Any	Any	xx (xx.x)	xx (xx.x)	xx (xx.x)	xx (xx.x)
Investigator	Any	xx (xx.x)	xx(xx.x)	xx (xx.x)	xx (xx.x)
	Erythema	xx (xx.x)	xx (xx.x)	xx (xx.x)	xx (xx.x)
	Scaling	xx (xx.x)	xx (xx.x)	xx (xx.x)	xx (xx.x)
	Dryness	xx (xx.x)	xx (xx.x)	xx (xx.x)	xx (xx.x)
Subject	Any	xx (xx.x)	xx (xx.x)	xx (xx.x)	xx (xx.x)
	Stinging/burning	xx (xx.x)	xx (xx.x)	xx (xx.x)	xx (xx.x)
	Itching	xx (xx.x)	xx (xx.x)	xx (xx.x)	xx (xx.x)

^a Percentages are based on the total number of patients safety population for the group.

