	(Min, Max)	(xxx,xxx)	(xxx,xxx)	(xxx,xxx)	(xxx,xxx)	(xxx, xxx)	(xxx, xxx)	
V14 –Week 44	n	XX	XX	XX	XX	XX	XX	
	Mean (SD)	xx.x (xx.xx)						
	Median	xxx.x	xxx.x	xxx.x	xxx.x	xxx.x	xxx.x	
	(Min, Max)	(xxx,xxx)	(xxx,xxx)	(xxx,xxx)	(xxx,xxx)	(xxx,xxx)	(xxx,xxx)	

^a Baseline is selected as the last measurement prior to the first application of study medication.

^b Includes early terminations or follow-ups collected during the first 26 weeks or during the additional six months for patients opting to continue treatment in the optional six month extension.

23 Apr 2019 Statistical Analysis Plan

Table 14.3.2.1
Vital Signs: Systolic Blood Pressure (mmHg)
Safety Population

		Fe	Female		Male		tal
Visit	Statistic	Value	Change	Value	Change	Value	Change
V15 – Week 48	n	XX	XX	XX	XX	XX	XX
	Mean (SD)	xx.x (xx.xx)					
	Median	XXX.X	XXX.X	XXX.X	XXX.X	XXX.X	XXX.X
	(Min, Max)	(xxx,xxx)	(xxx,xxx)	(xxx,xxx)	(xxx,xxx)	(xxx,xxx)	(xxx, xxx)
V16 – Week 52	n	xx	XX	XX	XX	XX	XX
	Mean (SD)	xx.x (xx.xx)					
	Median	XXX.X	XXX.X	XXX.X	XXX.X	XXX.X	XXX.X
	(Min, Max)	(xxx, xxx)	(xxx,xxx)	(xxx,xxx)	(xxx,xxx)	(xxx, xxx)	(xxx, xxx)
FU/Early Termination ^b	n	XX	XX	XX	XX	XX	XX
v	Mean (SD)	xx.x (xx.xx)					
	Median	xxx.x	xxx.x	xxx.x	xxx.x	xxx.x	xxx.x
	(Min, Max)	(xxx, xxx)	(xxx,xxx)	(xxx,xxx)	(xxx, xxx)	(xxx, xxx)	(xxx,xxx)

^a Baseline is selected as the last measurement prior to the first application of study medication.

^b Includes early terminations or follow-ups collected during the first 26 weeks or during the additional six months for patients opting to continue treatment in the optional six month extension.

Aclaris Therapeutics Inc. 23 Apr 2019
Protocol: ATI-50002-AGA-201 Statistical Analysis Plan

PROGRAMMING NOTE: to be repeated for the following:

Table 14.3.2.2	Vital Signs	Diastolic Blood Pressure	(mmHg) Safety Population
1 adic 14.5.4.4	vitai bigiis.	Diastone Dioou i ressure	(miming) Saicty i opulation

Table 14.3.2.3 Vital Signs: Heart Rate (bpm) Safety Population
Table 14.3.2.4 Vital Signs: Respiratory Rate (bpm) Safety Population
Table 14.3.2.5 Vital Signs: Temperature (Degrees C) Safety Population

23 Apr 2019 Statistical Analysis Plan

Table 14.3.3
ECG Interpretation: Shift from Baseline to Worst Assessment Post Baseline
Safety Population

Group	Worst Post-Baseline Interpretation, n (%)								
Baseline Interpretation	Normal	Abnormal, NCS	Abnormal, CS	Missing	Total				
Female (Na=xx)									
Normal	xx(xx.x)	xx (xx.x)	xx(xx.x)	xx (xx.x)	xx (xx.x)				

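### The only local skin reaction summary in the SAP shells is the worst post-baseline grade; it omits the Visit 2 grade and the by-visit summary that the protocol promises

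*SAP*

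**What the plan says.** Tolerability belongs to the primary objective: Protocol 6.1 sets out "to assess the safety, tolerability and efficacy of ATI-50002 Topical Solution". Under Protocol 12.1.6, investigators and subjects "assess the treated scalp area for local skin reactions (LSRs) at visits 2-11", grading five signs and symptoms (stinging/burning, itching, dryness, erythema, scaling) from 0 to 3. Protocol Table 3 continues the assessment at every extension visit through Visit 17.

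On reporting, the safety paragraph of the synopsis says: "Local skin reaction results will be tabulated and summarized by visit". Protocol 13.1 is broader: "Summary descriptive statistics (N, mean, median, SD) by visit will be provided for all safety and efficacy parameters". Protocol 13.4 does not repeat the LSR sentence, but nothing in it withdraws 13.1.

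The SAP's list of safety tables has one LSR entry, Table 14.3.1.8, "Highest Grade Any Time Post-Baseline". Its columns are mild, moderate, severe and total, for females, males and all subjects. Its rows are assessor and sign. The notes say "Patients are counted only once foreach sign at the highest severity grade" and "Percentages are based on the total number of patients safety population for the group". Grades by visit, from Visit 2 onward, are planned only in patient listing 16.2.3.5, which shows grades above 0.

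**The concern.** The trial has one open-label arm. With no vehicle group, each subject's own grade before treatment is the natural reference for later scalp signs. Table 14.3.1.8 makes no use of that grade, so a subject who arrives with mild dryness and keeps it unchanged is tabulated in the same cell as one whose dryness began on treatment.

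Collapsing all visits into one worst grade also removes time. A transient sting in week 3 and scaling present at every visit look alike. The table gives no number assessed, so a subject who left early counts in the denominator as if observed throughout.

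The adverse event tables do not close this gap. Protocol 12.1.6 requires an LSR to be recorded as an adverse event only if it needs treatment or leads to interruption or discontinuation. For milder signs, Table 14.3.1.8 is the only dedicated summary planned.

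**Working it through.** The plan gives no LSR figure to reproduce, so the main check compares commitment with delivery.

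**1. Commitment against shells**

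| Element | Protocol | SAP Table 14.3.1.8 |
|---|---|---|
| Summary by visit | Synopsis (LSR specifically); 13.1 (all safety parameters) | No visit rows |
| Visit 2 grade | Collected (12.1.6; Protocol Table 2) | Not shown |
| Grade 0 | Part of the scale (12.1.6) | No column |
| Number assessed | N by visit (13.1) | Whole safety population |

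**2. How the SAP treats other safety data**

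- Vital signs (Tables 14.3.2.1 to 14.3.2.5) have a baseline row and change at each visit. The laboratory tables (14.3.4.1 onward) follow the same format.
- ECG has "ECG Interpretation: Shift from Baseline to Worst Assessment Post Baseline" (Table 14.3.3).
- The adverse event listing marks events with onset before the first application as not treatment-emergent.
- LSR has none of these.

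**3. What the counting rule does**

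Take a subject with grade 1 dryness at Visit 2 and grade 1 at every later visit. The worst post-baseline grade is 1, so the subject is counted once under mild dryness. The change from Visit 2 is 1 − 1 = 0. The table reports the first number and never forms the second.

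**4. Illustrative size**

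Inputs: 24 planned subjects, 12 of each sex (Protocol 7.2). The proportion b with at least one grade 1 sign at Visit 2 is not in the documents and is assumed to be 10% to 40%. Each such sign is assumed to be graded again at one or more later visits.

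Subjects entering the table with no drug effect = 24 × b:

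- b = 10%: 24 × 0.10 = 2.4
- b = 20%: 24 × 0.20 = 4.8
- b = 40%: 24 × 0.40 = 9.6

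That is about 2 to 10 of 24. Within one sex column of 12 it is 12 × 0.10 = 1.2 to 12 × 0.40 = 4.8.

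**5. Is Visit 2 a usable baseline?**

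Visit 2 also includes clipping of the target area (9.2), the scalp tattoo (9.4) and the supervised first application (9.5). Neither the protocol nor listing 16.2.3.5 says whether the LSR grade precedes these. If it follows the application, it could already contain immediate stinging from the drug.

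**The case against.** The strongest reply is that nothing is lost. Listing 16.2.3.5 gives patient, visit, assessor, sign and grade, and with 24 subjects a reader can follow individual courses. This stands in part. A reader might infer that the trial cannot show whether reactions appear or fade; the documents do not support that, because the grades are collected and listed. The limit lies in the planned summary. A listing is still not the summary that the protocol promises. It also suppresses grade 0 and gives one entry to an assessor's signs whether all were 0 or not done, so the number assessed cannot be read from it.

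Second, the table does not call these signs drug-related or treatment-emergent. That is correct. The defect is that pre-existing and new signs are mixed under the heading of local skin reactions. It is not a formal attribution to the drug.

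Third, exclusion criterion 4 removes active scalp skin disease, which lowers the Visit 2 rate. It does not exclude mild dryness, scaling or itch short of disease.

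A reader might also infer that extension subjects will look less tolerant because they are graded more often. Table 14.3.1.8 has only female, male and total columns, so it makes no such comparison. Nor do the documents support a figure for how far repeated grading inflates the worst grade. That would need a background rate per rating and its correlation within subjects, and neither is given.

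Finally, no document promises a shift table for LSR. That is true: the by-visit summary is a commitment, and the shift is a recommendation. A shift to the worst grade would also still count new background signs as new or worsened.

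**Conclusion.** The concern holds as a gap between what the protocol commits to and what the SAP summarises. The visible SAP outputs have no by-visit LSR summary and no use of the Visit 2 grade. The one summary table counts unchanged pre-existing signs as local skin reactions.

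The size of about 2 to 10 subjects in 24 rests entirely on the assumed 10% to 40% with a persistent grade 1 sign at Visit 2. It shows scale and is not an estimate.

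Two limits apply. The SAP narrative was not in the text available, so any wording there on LSR handling could not be checked; the conclusion concerns the table list, shells and listings. Counting the off-drug follow-up in the worst grade is inferred from the title, which sets no on-treatment limit. The ECG table's note includes the post-treatment assessment explicitly, while the LSR table is silent.

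**What to change.** - Add a by-visit table for each sign, starting with Visit 2, giving counts at grades 0 to 3 and the number assessed.
- Add a shift table for each sign from the Visit 2 grade to the worst on-treatment grade, identifying grades above Visit 2 as new or worsened.
- Show the follow-up visit, four weeks after the last application, separately.
- State in the SAP that baseline is the Visit 2 grade recorded before the first application, and say whether it precedes clipping and tattooing. If the timing was not recorded, keep the worst-grade table alongside the shift and flag this limit.
- Add a note that the shift removes pre-existing signs but, without a control arm, cannot separate new background signs from drug effect.

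The cost is two added tables and a baseline definition, using data already scheduled for collection. No visit or procedure changes. The small downside is more output to review.
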